### 6.5.1. Allowed Therapy

During the study participants are requested to suspend their FIX prophylaxis regimen after infusion of PF-06838435, but may take:

- FIX replacement therapy is allowed, as needed. The infusion data (specific product, date, time, dosage, reason) is to be recorded in the eDiary.
- For a bleeding event, the investigator / study staff will recommend the appropriate dose of FIX to treat the bleed because the dose of factor concentrate should include the recent steady-state PF-06838435 induced FIX activity levels to avoid overdosing resulting in a potential thrombotic event. The table in [Appendix 8](#) provides guidelines for target FIX levels based on bleed type.
- A participant may resume prophylaxis if the PF-06838435 treatment is not efficacious, defined for this study as:
  - FIX activity after 12 weeks of  $\leq 2\%$  (in the absence of a confirmed FIX inhibitor) as determined by the central laboratory on 2 consecutive samples collected within a 2 week period;and/or
  - Over a 4-week period (in the absence of a confirmed FIX inhibitor);
    - 2 or more spontaneous bleeds into a major joint and/or target joint;or
    - 3 or more spontaneous bleeds (consisting of joint bleeds and/or significant soft tissue/muscle or other site bleeds). Significant spontaneous bleeds are defined as those that lead to a transient or persistent loss of function.

The investigator is to discuss the case with the sponsor's medical monitor prior to resumption of prophylaxis. Dosing of prophylaxis will take into account the current steady-state FIX activity level. A participant who resumes prophylaxis may choose to discontinue it; however, prior to discontinuation, the investigator is to discuss with the sponsor's medical monitor.

Additional allowed therapies include the following:

- COX-2 inhibitors and topical NSAIDs, where medically necessary
- HIV therapy

### **6.5.2. Disallowed Therapy**

The following concomitant medications are not permitted during the study:

- Blood products such as red blood cells (RBC), platelets, and fresh frozen plasma, except as required during a surgery or as clinically indicated in the setting of an emergency.
- Medications that may increase the risk of bleeding: such as anti-platelet agents (eg, aspirin, clopidogrel), anticoagulants (eg, warfarin, apixaban), regular long-term use of NSAIDs (eg, ibuprofen, naproxen). However, low dose aspirin (<100 mg/day) and PRN/short-term use of NSAIDs may be used where medically necessary. Please contact the sponsor's medical monitor if there are any questions regarding the use of medications that may prolong bleeding.
- Concomitant use of another investigational therapy; concurrent participation in another interventional clinical study is not allowed.
- Bypassing agents (eg, factor VIIA/ rFVIIA, activated prothrombin complex concentrate), except in situations where it is medically necessitated (ie, medical emergencies).

For COVID-19 vaccinations please refer to [Section 10.13.4](#).

### **6.6. Dose Modification**

No more than a single dose of the study treatment, on Day 1, will be administered during this study.

The dose of  $5 \times 10^{11}$  vector genomes/kg body weight will be modified for a participant with BMI >30 kg/m^2 (See the table in [Section 6.1](#)).

### **6.7. Intervention after the End of the Study**

No further intervention is planned after the end of the study.

## **7. DISCONTINUATION OF STUDY INTERVENTION AND PARTICIPANT DISCONTINUATION/WITHDRAWAL**

### **7.1. Discontinuation of Study Intervention**

Since no more than the single infusion of PF-06838435 on Day 1 will be administered during the study, this section is not applicable. See [Section 6.4](#) for any disruption in administration of the infusion.

## 7.2. Participant Discontinuation/Withdrawal from the Study

A participant may withdraw from the study at any time at his own request. Reasons for discontinuation from the study include the following:

- Refused further follow-up;
- Lost to follow-up;
- Death;
- Study terminated by sponsor;
- At the discretion of the investigator for safety, behavioral, compliance, or administrative reasons.

At the time of discontinuing from the study, if possible, an early discontinuation visit should be conducted, as shown in the [SoA](#). See [SoA](#) for any assessments to be collected at the time of study discontinuation and follow-up for any further evaluations that need to be completed.

The early discontinuation visit applies only to participants who are enrolled/randomized and then are prematurely withdrawn from the study. Participants should be questioned regarding their reason for withdrawal.

If a participant withdraws from the study, he may request destruction of any remaining samples taken and not tested, and the investigator must document any such requests in the site study records and notify the sponsor accordingly.

If the participant withdraws from the study and also withdraws consent (see Section 7.2.1) for disclosure of future information, no further evaluations should be performed and no additional data should be collected. The sponsor may retain and continue to use any data collected before such a withdrawal of consent.

Lack of completion of all or any of the withdrawal/early termination procedures will not be viewed as protocol deviations so long as the participant's safety was preserved.

When a participant withdraws from the study because of an SAE, the SAE must be recorded on the CRF and reported on the CT SAE Report.

### 7.2.1. Withdrawal of Consent

When a participant specifically withdraws consent for any further contact with him or persons previously authorized by the participant to provide this information, the participant should notify the investigator in writing of the decision to withdraw consent from future follow up, whenever possible. The withdrawal of consent should be explained in detail in the medical records by the investigator, as to whether the withdrawal is from study procedures and/or posttreatment study follow up, and entered on the appropriate CRF page. In the event that vital status (whether the participant is alive or dead) is being measured, publicly

available information should be used to determine vital status only as appropriately directed in accordance with local law.

### **7.3. Lost to Follow up**

A participant will be considered lost to follow-up if he repeatedly fails to return for scheduled visits and is unable to be contacted by the study site.

The following actions must be taken if a participant fails to return to the clinic for a required study visit:

- The site must attempt to contact the participant and reschedule the missed visit as soon as possible and counsel the participant on the importance of maintaining the assigned visit schedule and ascertain whether or not the participant wishes to and/or should continue in the study.
- Before a participant is deemed lost to follow up, the investigator or designee must make every effort to regain contact with the participant (where possible, 3 telephone calls and, if necessary, a certified letter to the participant's last known mailing address or local equivalent methods). These contact attempts should be documented in the participant's medical record.
- Should the participant continue to be unreachable, he will be considered lost to follow-up.
- Discontinuation of specific sites or of the study as a whole are handled as part of [Appendix 1](#).

## **8. STUDY ASSESSMENTS AND PROCEDURES**

- Study procedures and their timing are summarized in the [SoA](#). Protocol waivers or exemptions are not allowed; hence participants should follow the procedures as described in the study protocol.
- Immediate safety concerns should be discussed with the sponsor immediately upon occurrence or awareness.
- Adherence to the study design requirements, including those specified in the [SoA](#), is essential and required for study conduct.
- All screening evaluations must be completed and reviewed to confirm that potential participants meet all eligibility criteria. The investigator will maintain a screening log to record details of all participants screened and to confirm eligibility or record reasons for screening failure, as applicable.
- Procedures conducted as part of the participant's routine clinical management (eg, blood count) and obtained before signing of the ICF may be utilized for screening or baseline purposes, where indicated in the [SoA](#), provided the procedures

met the protocol-specified criteria and were performed within the time frame defined in the [SoA](#).

**The investigational sites for this study may be categorized as follows:**

- Study Site: Will screen and follow study participant post-infusion of PF-06838435 for the duration of the study. Some study sites may be approved to carry out infusions within their institution.
- Infusion Center: A site, external from the study site, approved for the administration of PF-06838435.

**Screening Period**

Screening procedures will be conducted according to the [SoA \(Section 1.3\)](#). The Screening Period will end and Baseline Period will commence when a participant is determined to be eligible for the study.

**Baseline Period and Scheduling the PF-06838435 Infusion**

Baseline procedures will be conducted according to the [SoA \(Section 1.3\)](#). PF-06838435 is to be ordered at the beginning of the Baseline Period after confirming eligibility. Prior to ordering IP, [Sections 10.13.3](#) and [10.13.4](#) should be considered. The IP will require approximately 3 weeks for shipment. Also, the timing of the participant's next FIX prophylaxis dose is to be planned to occur on the same day of PF-06838435 infusion (Day 1).

The Screening and Baseline period may be extended, upon consultation with the sponsor's medical monitor. Reason must be recorded in the source documents.

Study sites without necessary infusion facilities will complete Visit 2 at the Study Site and Visit 3 (Day 1) will be conducted at the designated Infusion Center.

**Day 1 (at Study Site or at approved Infusion Center)**

Day 1 procedures will be conducted according to the [SoA \(Section 1.3\)](#).

Blood for LFTs are to be drawn and tested locally and centrally prior to dosing participants (up to 3 days prior to Day 1/ Visit 3 is acceptable). Utilize mobile phlebotomy/ home health services as needed, and if possible. Local LFTs are required to be reviewed prior to thawing drug. If the investigator has any clinical concerns regarding the local LFT results, drug should not be thawed. These LFT results may help in the assessment of future LFTs and decisions on when to begin corticosteroid treatment, if necessary. These LFT results should be entered into the CRF as an unplanned visit.

Note: Participants should be informed that alcohol consumption could contribute to abnormally elevated LFT results and thereby delay the infusion of the study drug.

The site staff (or Infusion Center staff) will confirm that the participant is eligible (see [Section 5.1](#) and [5.2](#)) to receive PF-06838435 infusion. Prior to dosing, [Sections 10.13.3](#) and [10.13.4](#) should be considered. The IP should NOT be thawed and prepared without this eligibility confirmation AND affirming that the participant is physically present at the clinic (or infusion center).

Participants are expected to bring their current Factor IX replacement therapy with them.

If the infusion of PF-06838435 is started for a participant and cannot be completed (receives less than the prescribed dose) for any reason, the protocol does not allow for the participant to be rescreened. The participant will be followed for safety; the data obtained from such participant will not be included towards efficacy assessment.

For Japanese sites please refer to Japan appendix, [Section 10.11.1.4](#).

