## 6.4. Study Intervention Compliance

Study treatment will be infused via infusion pump on Day 1 under supervision by the site staff. The vial lot number, total volume, and infusion time (start and stop times) will be monitored and recorded by the site staff. Full compliance with study treatment infusion is anticipated. Prior to dosing, [Sections 10.13.3](#) and [10.13.4](#) should be considered. For Japanese sites please refer to Japan appendix, [Section 10.11.1.4](#).

**Administration:** If a participant does not receive a complete infusion for any reason, he will not be rescreened, but will be followed for safety.

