## 9.3. Populations for Analyses

For purposes of analysis, the following populations are defined:

Population	Description
Enrolled	All participants who sign the ICF and meet all inclusion/exclusion criteria.
Dosed 	All participants enrolled in the study and received IP.
Safety	All participants enrolled in the study and received IP, which is the same as dosed population.
Intent To Treat (ITT)	ITT population is not defined for this study since it is not a randomized study.
Evaluable	All participants are enrolled in the study and take study medication and no significant interruption of efficacy measurement. 

1. Dosed population is the primary analysis population for efficacy endpoint analysis, while evaluable population is the analysis population for sensitivity analysis.
2. Significant interruption will be assessed after discussion between the investigator and the medical monitor, eg, if a participant requires a major surgery, this will be a significant interruption of measurement.

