4. ANALYSIS SETS (POPULATIONS FOR ANALYSIS)

This study is an open-label, single-arm study. The populations for analyses are outlined in the table below.

Population	Description
Enrolled	All participants who sign the informed consent form (ICF) and meet all inclusion/exclusion criteria
Dosed	All participants enrolled in the study and who received PF-06838435 infusion
Safety	All participants enrolled in the study and who received PF-06838435 infusion, which is the same as dosed population.
Evaluable	All participants enrolled in the study and who received PF-06838435 infusion and have no significant interruption of efficacy measurement.

The Evaluable analysis population listed above would exclude participants with significant interruption of efficacy measurement, or participants who do not have or have not yet completed 15 months of follow up post PF-06838435 infusion. Significant interruption will be assessed after discussion between the investigator and the medical monitor, e.g., if a participant requires a major surgery, this will be a significant interruption of measurement.

In this study, there are also substudies planned, for which the analysis populations are outlined below.

X-ray Substudy	All dosed participants sign the additional ICF for the X-ray substudy and meet all
Analysis Population	inclusion/exclusion criteria, and the participant's joint images have been
	reviewed.
MRI Substudy	All dosed participants who are dosed and sign the additional ICF for the MRI
Analysis Population	substudy and meet all inclusion/exclusion criteria, and the participant's joint
	images have been reviewed following the extended MRI scale with a final score
	combining soft-tissue and osteochondral sub-scores at baseline, and any data
	post-baseline
Vector Shedding	All dosed participants who sign the additional ICF for the Vector Shedding
Substudy Analysis	substudy and meet all inclusion/exclusion criteria, and who have any additional
Population	vector shedding data

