6. ANALYSES AND SUMMARIES

6.1. Primary Endpoint(s)

6.1.1. ABR for Total Bleeds

6.1.1.1. Main Analysis

ABR_{total} will be analyzed using a repeated measures generalized linear model with negative binomial distribution and identity link function. Treatment (prophylaxis, or PF-06838435) and duration will be included in the model. Treatment will be a class factor in the model, duration is numeric and participant will be a random effect. Duration is the elapsed time in years of each treatment period. Duration is at least 0.5 for pre-PF-06838435 infusion prophylaxis which corresponds to six months. This period begins at enrollment of the lead-in study and ends on date of PF-06838435 infusion. Duration of PF-06838435 period is the observed time from Week 12 (Day 82) until cutoff for the specified analysis (e.g. 15 months for the primary analysis) or the date of study withdrawal or resumption of FIX infusion (whichever is earlier), minus any time that is predefined to be excluded.

- The Dosed population will be the primary analysis population. Analysis will be repeated for the Evaluable population if it is different from Dosed population.
- The mean ABR_{total} from Week 12 to Month 15 will be compared to the pre-infusion mean via the estimation of the mean difference and 95% CI. If the upper bound of the confidence interval of the difference of (ABR_{total} PF-06838435 ABR_{total} FIX prophylaxis) is smaller than 3.0, then statistical significance of the noninferiority claim would be demonstrated. An example of SAS code of such analysis is included in the Appendix 1.1. If noninferiority is demonstrated, further testing for superiority would be conducted after the primary analysis (assuming other endpoints within the

testing hierarchy are statistically significant), using the same method, except the margin would be modified to 0.

• The summary table will include two columns, for FIX prophylaxis and PF-06838435, respectively. The summary statistics in the table will include n, mean, median, Q1, Q3, range of the observed ABR_{total}, model derived mean ABR_{total} and 95% CI, estimated mean difference (model derived), and the 95% CI of the mean difference (model derived).

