6.5.3. Study Treatment Exposure

PF-06838435 infusion information will be summarized in the Dosed population. Duration of infusion, and total dose of PF-06838435 (in vector genomes [vg] and vector genomes per kilogram [vg/kg]), whether actual dose was adjusted from planned will be summarized.

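### Protocol Section 8 bars incompletely infused participants from efficacy, while the primary Dosed set includes them, and neither document says which rule governs

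*Protocol*

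**What the plan says.** **The exclusion.** Protocol Section 8, under Day 1, covers a participant whose infusion is started and then cannot be completed, for whatever reason, so that he receives less than the prescribed dose. He may not be rescreened and is followed for safety, and "the data obtained from such participant will not be included towards efficacy assessment". Protocol 6.4 covers the same event but stops at safety follow-up: "If a participant does not receive a complete infusion for any reason, he will not be rescreened, but will be followed for safety". It does not mention efficacy.

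**The primary set.** A footnote to the table in Protocol 9.3 says "Dosed population is the primary analysis population for efficacy endpoint analysis". The same table defines the Safety set as "All participants enrolled in the study and received IP, which is the same as dosed population". SAP Section 4 defines Dosed as "All participants enrolled in the study and who received PF-06838435 infusion", and SAP 6.1.1.1 says of total bleeds, "The Dosed population will be the primary analysis population". The SAP's primary estimand (2.1.1) takes as its population men who have received the infusion, and it does not name an incomplete infusion as an intercurrent event.

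**The Evaluable set.** SAP Section 4 requires that participants "have no significant interruption of efficacy measurement", and also excludes those without 15 months of follow-up. An incomplete infusion is not among the criteria.

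**The concern.** For a participant with an incomplete infusion, the documents give two instructions that cannot both be followed. Section 8 removes him from efficacy; the population definitions put him in the primary efficacy analysis.

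The trial is open-label with a single arm, and Protocol 9.5 and SAP 7.1 allow the sponsor to review data during the study for safety. If such a case arises and is not settled beforehand, the choice of rule could be made with his bleeding record known. Following Section 8 would also drop a treated man from the population that the estimand names, and from the key secondary endpoints analysed in Dosed. Two of those endpoints otherwise count failures: FIX:C is imputed at 1.9% after dropout or resumed prophylaxis, and AIR counts every infusion.

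**Working it through.** **Can the texts be reconciled?**

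1. One could read receipt of the product as meaning a complete infusion. Both documents equate Safety with Dosed, so that reading would take incompletely infused men out of the safety analysis, although Section 8 says they are followed for safety.
2. If they are in Safety, they are in Dosed, and therefore in the primary efficacy analysis that Section 8 closes to them.
3. The Evaluable set does not settle the matter, because its criteria concern interrupted measurement and length of follow-up.
4. SAP 6.5.3 reports dosing within Dosed, where "whether actual dose was adjusted from planned will be summarized". The SAP thus allows for dose variation in that set, but it neither carries over nor cancels the Section 8 rule.

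**Inputs for size.** Protocol 9.2 gives N = 40, rates of 5.0 before and 1.5 after infusion, a margin of 3.0 and one-sided alpha of 0.025. The expected difference is 1.5 − 5.0 = −3.5, and the gap to the margin is 3.0 − (−3.5) = 6.5. The pre-infusion period is at least 0.5 year (SAP 6.1.1.1). The post-infusion period is Day 82 to Day 469, so 388/365.25 = 1.062 years (SAP 5.2).

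**The plan's power figure.** The stated power of at least 90% cannot be reproduced exactly, because the documents give no negative binomial dispersion k. With a paired normal approximation and independent periods:

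SD = √(5/0.5 + 25k + 1.5/1.062 + 2.25k)

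Power = Φ(6.5·√N/SD − 1.96)

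| Assumed k | SD | N = 40 | N = 39 | N = 38 |
|---|---|---|---|---|
| 2 | 8.12 | 99.9% | 99.9% | 99.9% |
| 4 | 10.97 | 96.3% | 95.9% | 95.5% |
| 5 | 12.15 | 92.3% | 91.6% | 91.0% |
| 6 | 13.23 | 87.5% | 86.6% | 85.8% |

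The 90% claim holds at N = 40 when SD ≤ 6.5·√40/(1.96 + 1.28) = 12.7, or k up to about 5. A simulation of the paired difference with independent periods gave higher power at the larger dispersions (99.7% at k = 4 and 97.8% at k = 6, N = 40). Excluding a participant costs about one point of power or less.

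**Effect on the estimate.** Suppose m of 40 men have incomplete infusions and an ABR change of d, while the others average −3.5. Retaining them shifts the mean difference by m(d + 3.5)/40. The values of d are assumptions.

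| d | m = 1 | m = 2 |
|---|---|---|
| 0 | 0.09 | 0.18 |
| +5 | 0.21 | 0.43 |
| +10 | 0.34 | 0.68 |
| +20 | 0.59 | 1.18 |

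**Effect on the confidence bound.** A poor outcome also widens the interval. Take SD = 8.12 (k = 2) in the other men.

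- **Two men excluded:** upper bound −3.5 + 1.96 × 8.12/√38 = −0.92.
- **Two men retained, d = +20:** mean −3.5 + 1.175 = −2.325. SD = √[(37 × 8.12² + (38 × 2/40) × 23.5²)/39] = 9.46. Upper bound −2.325 + 1.96 × 9.46/√40 = 0.61.

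Both bounds are well below 3.0, but only the first is below 0. With one man at d = +20, the same steps give −0.17 retained and −0.95 excluded, so neither conclusion changes.

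**The case against.** The strongest reply is that the question is already answered. Protocol 9.4 leaves the analysis populations to the SAP. The SAP (version 6.0, 07 Jul 2022) is later than the protocol amendment (29 Jun 2022), may modify protocol plans, and requires departures from itself to be described in the study report. It names Dosed without a completeness condition. On that reading the man is included, and dropping him would be a reportable deviation. This points towards inclusion but falls short of an explicit rule: the SAP never mentions the Section 8 exclusion, and its Section 2 says major changes to the primary analysis will also appear in a protocol amendment.

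A reader might infer that the sponsor could drop poor responders at will. The documents do not support that. The exclusion is pre-specified, it turns on receiving less than the prescribed dose, and infusion volume and times are recorded on Day 1 (Protocol 6.4), before the efficacy window opens on Day 82. Only the choice between two written rules is open.

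A reader might also infer that an incomplete infusion predicts a poor outcome. The documents contain no partial-dose results, and an infusion stopped near its end delivers almost the full dose. A man who bled often might also meet the criteria for resuming prophylaxis in Protocol 6.5.1. His later bleeds and time would then leave the ABR calculation (SAP 3.1.1), and he would count for less than one fortieth of a simple mean. These points stand, and they limit the size of the problem.

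Finally, a separate efficacy set requiring a complete infusion, no longer tied to Safety, would also remove the contradiction. That is true, but it would depart from the estimand population the SAP already states.

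**Conclusion.** The contradiction is real, and it exists within the protocol as well as between protocol and SAP. Section 8, if followed, would break the stated primary population and estimand. Correcting it is worthwhile but does not decide whether the trial can succeed. Protocol 6.4 anticipates full compliance with the infusion, so the number affected may be zero.

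Under the planning rates, one or two cases are unlikely to alter the non-inferiority conclusion. Superiority at margin 0, later in the SAP 5.1 hierarchy, is more sensitive: in the illustration it changed with two men at an extreme assumed outcome and not with one. A true effect smaller than planned would also leave less room. All sizes rest on assumed dispersion and assumed individual outcomes, and on a paired approximation in place of the planned negative binomial model.

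**What to change.** Before database lock:

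- State in SAP 4 that anyone who received any amount of PF-06838435 belongs to the Dosed set and enters the primary analysis.
- Reword the Day 1 text in Protocol Section 8 so that its exclusion applies only to a supportive analysis, and align Protocol 6.4 with it.
- Specify that, if any incomplete infusions occur, the ABR and key secondary analyses are repeated without those participants.
- List each case with the planned and delivered dose.

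The cost is a few sentences in each document and one conditional repeat analysis. No new data are needed, since infusion volume and times are already recorded.
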